6.7.2 Dosing Modification Guidance and Stopping Criteria

6.7.2.1 Dose Delays and Interruptions for GEN1053 or GEN1053+IM

The methodology for dose escalation is provided in Sections 4.2.1 and 4.2.2.

No intrasubject dose de-escalation will be allowed. The doses of GEN1053 or IM cannot be reduced but may be delayed.

- Administration of trial treatment can be delayed for up to 21 days (ie, 1 cycle) unless otherwise approved by the sponsor medical monitor. If the severity resolves to ≤ grade 1 or baseline within this period, retreatment may be considered under the following conditions:
 - In case of safety concerns, and for subjects who experience a recurrence of the same AEs of < grade 3 severity with rechallenge of GEN1053 or GEN1053+IM, a consultation between the sponsor and investigator will occur to determine whether the subject should continue trial treatment at the same schedule or whether the dosing interval in subsequent cycles should be increased. The sponsor may also consult the DMC as specified in Appendix 1.
 - A subject who experiences the same AE of \geq grade 3 with rechallenge of GEN1053 or GEN1053+IM must discontinue trial treatment immediately.
- For subjects receiving GEN1053+IM combination therapy, both GEN1053 and IM should be withheld or discontinued. Subjects may only continue GEN1053 or IM monotherapy if approved by the sponsor.

Decisions regarding dosing modification of trial treatment should be made using clinical judgment, considering relatedness of the AE to the trial treatment and the subject's underlying condition. For guidance, please see Table 6-2. The investigators are encouraged to contact sponsor in case of any safety concern that needs thorough discussion and evaluation.

Note that specific rules apply for irAEs, thrombocytopenia, neutropenia, CRS, and IRRs (see Sections 6.7.2.2 and 6.7.2.3).

Table 6-2 Dosing Modification and Management of Treatment-Related AEs

CTCAE Grade/Severity	Hold Treatment (Y/N)	Dosing Modification
Grade 1 or Grade 2 (Mild or moderate)	Ν	Continue treatment at the discretion of the investigator. If thrombocytopenia \geq grade 2 is identified, with or without bleeding, further treatment should be interrupted (see Section 6.7.2.3).
Grade 3 (Severe)	Y	Withhold treatment until resolution to \leq grade 1 or baseline
Grade 4 (Life-Threatening)	Y	Permanent discontinuation except if approved by medical monitor. If continuing on treatment, toxicity must resolve to grade 1 or baseline.

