6.7.2.2 Toxicity Management for Immune-Related AEs

AEs associated with GEN1053 or GEN1053+IM may represent an irAE. Immune CPIs are associated with a spectrum of adverse effects related to the immune-mediated MoA and are different from other systemic therapies such as cytotoxic chemotherapy **CC** Guidance for dose modification and management of irAEs is provided in Table 6-3. For additional guidance on the recommended management of irAEs, please refer to the **CC**

General Guidance

Additional procedures or tests such as bronchoscopy, endoscopy, or skin biopsy may be included as part of the evaluation.

- Based on the severity of irAEs, trial treatment should be withheld or permanently discontinued, and corticosteroids administered.
- For severe and life-threatening irAEs, IV corticosteroid should be initiated first followed by oral steroid. Other immunosuppressive treatment should be initiated if irAEs cannot be controlled by corticosteroids (also see Table 6-3).
- Corticosteroid taper should be initiated upon AE improving to grade 1 or less continue to taper over at least 4 weeks.
- GEN1053 or GEN1053+IM may be resumed after the AE has resolved to ≤ grade 1. Note: The corticosteroid dose must be ≤10 mg/day before treatment is resumed.
- For grade 1 irAEs, trial treatment should be continued with close monitoring unless otherwise noted in Table 6-3.
- For > grade 1 irAEs, withhold treatment until resolution to ≤ grade 1 unless otherwise specified in Table 6-3.
- Permanent discontinuation of trial treatment is recommended for grade 4 toxicities with the exception of endocrinopathies that have been controlled by hormone replacement.
- Trial treatment should also be permanently discontinued for any serious grade 3 irAE that recurs and for any life-threatening irAE. Also consider permanently discontinuing trial treatment for grade 3 AST, ALT, or bilirubin increases (see Table 6-3 for details).

Table 6-3	Dosing Modification and Management of Immune-Related Adverse Events	
-----------	---	--

Immune-Related AEs	Toxicity Grade (CTCAE v5.0)	Dose Modification	Guidance for Management of irAEs
Pneumonitis	Grade 1	Withhold treatment or proceed with close monitoring.	Monitor for signs and symptoms of pneumonitis. Evaluate for pneumonitis with radiographic imaging. For ≥ grade 2: Administer corticosteroids (initial dose of 1 to 2 mg/kg prednisone or

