	Grade 2	Withhold treatment until resolution to \leq grade 1 and corticosteroid has been tapered ^a	equivalent) followed by taper. Consider bronchoscopy with BAL±transbronchial biopsy. Add prophylactic antibiotics for opportunistic infections.
	Grade 3 or Grade 4	Permanently discontinue	For \geq grade 3: Administer methylprednisolone IV 1-2 mg/kg.
Colitis	Grade 2	Withhold treatment until resolution to \leq grade 1 and corticosteroid has been tapered ^a	Monitor for signs and symptoms of colitis. Consider gastroenterology consultation and confirm diagnosis of colitis. Endoscopic evaluation
	Grade 3	Withhold treatment until resolution to \leq grade 1 and corticosteroid has been tapered ^a	for cases grade 2 or higher. Administer corticosteroids (initial dose of 1 to 2 mg/kg prednisone or
	Grade 4	Permanently discontinue	equivalent) followed by taper. Consider adding infliximab or vedolizumab if inadequate response. Grade 4: Administer 1-2 mg/kg methylprednisolone IV or equivalent followed by taper.
Hepatitis (ALT, AST, or bilirubin increased)	Grade 2 (asymptomatic)	Withhold treatment until resolution to \leq grade 1 and corticosteroid has been tapered ^a	Initiate work-up for other causes of elevated liver enzymes such as viral hepatitis, alcohol history, iron study, thromboembolic event, liver ultrasound, and cross-sectional imaging for potential liver metastasis. Liver function tests must be monitored closely, the first time within 48 hours, and at least twice per week (unscheduled visits) for up to 4 weeks until resolution to \leq grade 1. Consider immediate administration of corticosteroids (initial dose of 0.5-1 mg/kg prednisone or equivalent) or at the latest within 3 days if no improvement, followed by taper. For AST or ALT elevations \geq grade 2 with concomitant bilirubin $>2.0 \times$ ULN with no signs of cholestasis, ie, a Hy's law case, permanently discontinue.

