	Grade 3 or symptomatic	 Permanently discontinue if symptomatic Withhold treatment until resolution to ≤ grade 1 and corticosteroid has been tapered If the grade 3 AST, ALT, or bilirubin increase resolves to ≤ grade 1 within 14 days, trial treatment may be continued after sponsor medical monitor approval 	Initiate work-up for other causes of elevated liver enzymes such as viral hepatitis, alcohol history, iron study, thromboembolic event, liver ultrasound, and cross-sectional imaging for potential liver metastasis. Monitor liver function tests (unscheduled visits) twice per week for up to 4 weeks until resolution to \leq grade 1.

Immune-Related AEs	Toxicity Grade (CTCAE v5.0)	Dose Modification	Guidance for Management of irAEs
		 If the grade 3 AST, ALT, or bilirubin increase does NOT resolve to ≤ grade 1 within 14 days, permanently discontinue trial treatment 	Immediately administer corticosteroids (grade 3: initial dose of 1-2 mg/kg methylprednisolone IV or equivalent; Grade 4: 2 mg/kg methylprednisolone IV or equivalent) followed by taper.
	Grade 4	Permanently discontinue	Consider adding prophylactic antibiotics for opportunistic infections. If no improvement within 3-5 days despite methylprednisolone IV or equivalent is observed, consider prompt treatment with immunosuppressive therapy (eg, mycophenolate mofetil at 500 mg every 12 hours; discuss with medical monitor).
			Infliximab should not be used.
			Hepatology consult, abdominal workup, and imaging as appropriate.
T1DM or Hyperglycemia	Newly diagnosed T1DM or Grade 3-Grade 4 hyperglycemia	Withhold until glucose control is obtained ^{b,c}	Monitor for hyperglycemia or other signs and symptoms of diabetes. Consider endocrine consultation. Consider administration of insulin for type 1 diabetes. Consider administration of antihyperglycemic agents in subjects with hyperglycemia.
Hypophysitis	Grade 2	Continue treatment at the discretion of the investigator	Monitor for signs and symptoms of hypophysitis. Consider endocrine
	Grade 3 or Grade 4	Withhold until subject is stabilized on replacement therapy or permanently discontinue ^b	consultation. Consider administration of corticosteroids and initiate hormonal replacements as clinically indicated. Corticosteroid taper should be initiated upon irAE improving to grade 1 or less.
Hypothyroidism	Grade 2	Continue treatment at the discretion of the investigator	Consider endocrine consultation

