	Grade 3-Grade 4	Withhold until symptoms resolve to baseline with appropriate supplementation	Prescribe thyroid hormone supplementation in symptomatic subjects with any degree of TSH elevation or in asymptomatic subjects with TSH levels that persist.>10 mIU/L (measured 4 weeks apart)
Hyperthyroidism	Grade 2	Continue treatment at the discretion of the investigator	Monitor for signs and symptoms of thyroid disorders.
	Grade 3-Grade 4	Withhold until symptoms resolve to baseline with appropriate therapy consultation or permanently discontinue ^{b,c}	Consider management with thionamides and beta-blockers as appropriate.
Nephritis and renal dysfunction	Grade 1	Consider temporary hold pending consideration of baseline renal function and to confirm etiology ^a	Monitor subjects for elevated or changes in serum creatinine before every dose.
	Grade 2	Withhold treatment until resolved to baseline ^a	For \geq grade 2: If worsening or no improvement, consider
	Grade 3-Grade 4	Permanently discontinue	administration of corticosteroids (prednisone 0.5 to 2 mg/kg or equivalent) followed by taper. Corticosteroid taper should be initiated upon irAE improving to grade 1 or less. Consider nephrology consultation.
Cutaneous toxicities	Grade 1 or Grade 2	Continue treatment at the discretion of the investigator	Based on the severity of the skin toxicity, consider administration of
	Grade 3	Withhold treatment until resolved to \leq grade 1^a	corticosteroids. Corticosteroid taper should be initiated upon irAE
	Grade 4	Permanently discontinue	improving to grade 1 or less.

Immune-Related AEs	Toxicity Grade (CTCAE v5.0)	Dose Modification	Guidance for Management of irAEs
			For signs or symptoms of SJS or TEN, withhold and refer the subjects for specialized care. Monitor closely for improvement regardless of grade. If SJS or TEN is confirmed, permanently discontinue.
For other ^d	Grade 2 Grade 3	Continue treatment at the discretion of the investigator Withhold or permanently discontinue ^b	Based on type and severity of AE, consider administration of corticosteroids. Permanently discontinue for any grade 3 irAE that recurs and for any life-threatening irAEs.

AE=adverse event; ALT=alanine aminotransferase; AST=aspartate aminotransferase; BAL=bronchoalveolar lavage; CTCAE=Common Terminology Criteria for Adverse Events; irAE=immune-related adverse event; SJS=Stevens-Johnson syndrome; T1DM=type 1 diabetes mellitus; TEN=toxic epidermal necrolysis; TSH: thyroid-stimulating hormone.

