a. The next dose of trial treatment can maximally be delayed 21 days unless approved otherwise by the sponsor medical monitor. If irAE resolves within 21 days to baseline, restart treatment at the same dose level after consulting the sponsor medical monitor.

b. Investigator must contact the sponsor to discuss whether the subject should be withdrawn from trial treatment or if the next dose should be delayed. Subjects may be treated with the same dose and schedule. The sponsor may also consult the DEC as specified in Appendix 1.

c. For subjects with grade 3 or 4 immune-related endocrinopathy leading to withholding of trial treatment dosing, treatment may be resumed when the AE recovers to \leq grade 2 and is controlled with hormonal replacement therapy or achieved metabolic control (in case of T1DM).

d. Refer to CCI reference for guidance on immune-related musculoskeletal, nervous system, hematologic, cardiovascular, ocular and specific cutaneous toxicities.

Attribution of Toxicity

When GEN1053 is administered in combination with IM (GEN1053+IM), attribution of an AE to a single component is likely to be difficult. Therefore, while the investigator may attribute a toxicity event to GEN1053, IM or both for AEs listed in Table 6-3, both treatment with GEN1053 and IM must be withheld according to the recommended dosing modifications in Section 6.7.2.1.

If the toxicities do resolve and conditions are aligned with what is defined in Table 6-3, GEN1053+IM combination therapy may be restarted at the discretion of the investigator. Reinitiation of either GEN1053 or IM as monotherapy may only be considered after communication with and approval by the sponsor.

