6.7.2.4 Safety Stopping Rules for Trial Treatment

Treatment with trial treatment should be discontinued due to safety concerns under the following conditions:

- Subjects experiencing a DLT (refer to Section 6.7.1) should discontinue trial drug immediately. If requested by the investigator, the sponsor may allow a subject with a DLT to continue in the trial. For this decision, a thorough benefit-risk assessment of the individual subject is required, and consultation of the DMC may be considered.
- If a subject experiences a toxicity that would have qualified as a DLT, but that occurs after the DLT evaluation period, the subject's benefit-risk must be thoroughly assessed. Continued treatment with GEN1053 and/or IM must be agreed between the sponsor and the investigator.
- If the subject experiences a TRAE that meets the criteria for treatment discontinuation as specified in Sections 6.7.2.2 and 6.7.2.3 and Table 6-3 and Table 6-4.
- An AE that fails to resolve to \leq grade 1 within 21 days due to a toxicity possibly related to trial drug, unless otherwise approved by the sponsor medical monitor.
- Treatment-related grade 4 or life-threatening AE, except with approval from the medical monitor.
- Second occurrence of an IRR of \geq grade 3 despite premedication prior to the second infusion.
- First occurrence of anaphylaxis or a grade 4 IRR.
- Subjects with grade 4 transaminase or bilirubin elevation.
- Subjects with abnormal liver function parameters that meet Hy's law criteria as defined in Section 6.7.1.
- In case of thrombocytopenia not resolving to ≤ grade 1 within 21 days after the planned dosing date, unless approved otherwise by the sponsor.
- If the subject experiences grade 4 thrombocytopenia or grade 3 thrombocytopenia with clinically significant bleeding.
- First episode of CRS grade 4.
- First episode of cytokine blockade-refractory grade 3 CRS lasting >72 hours.

Note:

• Subjects should, whenever possible, irrespective of the reason for discontinuation, be examined as soon as possible for details regarding discontinuation of treatment (refer to Section 7.1).

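### Recurrent grade 3 irAEs fall under conflicting stopping rules, and the colitis, liver and cutaneous rows of Table 6-3 allow full-dose redosing with no recurrence rule

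*Combined protocol and SAP*

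**What the plan says.** A grade 3 irAE that comes back after redosing is addressed in three places.

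- Section 6.7.2.1 states that a subject with the same AE at or above "grade 3 with rechallenge of GEN1053 or GEN1053+IM must discontinue trial treatment immediately". It then adds: "Note that specific rules apply for irAEs, thrombocytopenia, neutropenia, CRS, and IRRs", pointing to 6.7.2.2 and 6.7.2.3. The same section rules out dose reduction.
- The general guidance in 6.7.2.2 states: "Trial treatment should also be permanently discontinued for any serious grade 3 irAE that recurs and for any life-threatening irAE".
- The last row of Table 6-3, for irAEs not otherwise named, states: "Permanently discontinue for any grade 3 irAE that recurs and for any life-threatening irAEs".

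Three named rows of Table 6-3 allow treatment to resume after grade 3:

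- **Colitis:** treatment is held until the event is at or below "grade 1 and corticosteroid has been tapered".
- **Cutaneous toxicity:** treatment is held until grade 1 or lower. This row and the colitis row carry footnote a: "If irAE resolves within 21 days to baseline, restart treatment at the same dose level after consulting the sponsor medical monitor".
- **Liver:** if an asymptomatic grade 3 AST, ALT or bilirubin rise returns to grade 1 or lower within 14 days, "trial treatment may be continued after sponsor medical monitor approval".

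The subject-level stopping list in 6.7.2.4 brings in the irAE rules by reference, through a "TRAE that meets the criteria for treatment discontinuation as specified in Sections 6.7.2.2 and 6.7.2.3 and Table 6-3 and Table 6-4". Section 7.1 sends the reader to 6.7.1 and 6.7.2.4 for AE-related discontinuation.

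**The concern.** The three rules give different answers for the same event. Under 6.7.2.1 and the last row of Table 6-3, any recurrence at grade 3 ends treatment. Under the 6.7.2.2 bullet, only a serious one does.

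The three redosing rows are not merely silent. They grant a permission that is not confined to a first occurrence, and the stopping list never leads the reader back to 6.7.2.1. A site or monitor working from the irAE text could redose a subject whom another section says must stop. Because dose reduction is prohibited, that redosing would be at the full dose.

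The liver row has practical relevance. Section 2.3.2.1 reports severe transaminase increases in phase 1a among subjects with anti-PD-1/PD-L1 exposure in the preceding 6 months.

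**Working it through.** No statistical quantity is involved, so the check compares the provisions and follows one case through them.

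**Step 1. The recurrence rules side by side**

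| Place | Trigger | Seriousness needed? | Force |
|---|---|---|---|
| 6.7.2.1 | Same AE at grade 3 or above on rechallenge | No | Must stop immediately |
| 6.7.2.2 bullet | Grade 3 irAE recurs | Yes | Should stop permanently |
| Table 6-3, last row | Grade 3 irAE recurs | No | Stop permanently |

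The 6.7.2.1 note on specific rules can be read two ways. If it gives 6.7.2.2 precedence, a recurrent non-serious grade 3 irAE meets a weaker rule than any other recurrent grade 3 AE, and 6.7.2.2 still disagrees with its own table. If it does not, the redosing rows permit what 6.7.2.1 forbids. Neither reading is free of conflict.

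**Step 2. How many Table 6-3 rows are affected**

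- Named irAEs: 9 (pneumonitis, colitis, hepatitis, type 1 diabetes or hyperglycemia, hypophysitis, hypothyroidism, hyperthyroidism, nephritis, cutaneous).
- Permanent stop at the first grade 3 event: 2 (pneumonitis, nephritis).
- Endocrine rows with their own handling: 4.
- Remaining rows that allow redosing after grade 3: 9 − 2 − 4 = 3 (colitis, liver, cutaneous).
- Of those 3, rows that state a recurrence rule: 0.

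**Step 3. What the stopping list reaches**

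Section 7.1 leads to 6.7.1 and 6.7.2.4. Section 6.7.2.4 cites 6.7.2.2, 6.7.2.3, Table 6-3 and Table 6-4, but not 6.7.2.1, and has no general item for a grade 3 recurrence on rechallenge. For the three rows, the only recurrence trigger reached this way is the 6.7.2.2 bullet limited to serious events. Recurrence rules are written out elsewhere: a second IRR of grade 3 or higher (6.7.2.4) and more than two interruptions for thrombocytopenia (6.7.2.3).

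**Step 4. Worked case**

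Assume an asymptomatic, non-serious grade 3 ALT rise, judged to be an irAE and not a Hy's law case. It resolves within 14 days, the subject is redosed, and it recurs at grade 3.

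- 6.7.2.1: stop immediately.
- 6.7.2.2 bullet: not triggered, because the event is not serious.
- Liver row: if it again resolves within 14 days, redosing is again open with monitor approval.
- Last row of Table 6-3: would require a stop, if its wording is taken to reach beyond unnamed irAEs.

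**Step 5. Whether seriousness changes the action**

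It can. Section 8.3.6 and Appendix 3 both say that a grade 3 or 4 laboratory abnormality is not by itself an SAE.

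**The case against.** The best case for the current text is that its rules can be reconciled. The 6.7.2.2 bullet says when to stop; it does not say that a non-serious recurrence may be redosed. Section 6.7.2.1 contains no irAE exception, and a site that follows it satisfies every provision. The attribution paragraph under Table 6-3 refers to 6.7.2.1 for withholding both drugs, which suggests the drafters thought 6.7.2.1 applied to these events. Recurrence can be set in general text without being repeated in each row.

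There are also other safeguards:

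- Redosing needs medical monitor consultation or approval.
- Steroids must be down to 10 mg/day or less before resumption. The taper runs at least 4 weeks (28 days) against a 21-day cap on delay, so many steroid-treated cases will need an individual monitor decision anyway.
- Symptomatic grade 3 liver events and Hy's law cases stop permanently.
- Section 6.7.2.2 asks investigators to consider stopping for grade 3 liver increases.
- DLT-type events after the DLT period need a benefit-risk assessment and sponsor agreement.

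Finally, Section 5.2 now excludes subjects with anti-PD-1/PD-L1 treatment within 6 months, medically significant events already count as serious, and some cited irAE guidance is redacted.

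Most of these points are factually right, and they limit how often the conflict will matter. They do not remove it. The attribution paragraph is written for combination therapy and concerns withholding. If it does show that 6.7.2.1 applies to Table 6-3, it makes the row permissions contradictory. The sentence on considering discontinuation for liver increases is discretionary. The late-DLT item requires an assessment, not a stop, and the DLT criterion for liver tests in 6.7.1 does not capture a grade 3 rise that recovers within 14 days. Monitor review does not settle the matter, because the monitor faces the same conflicting text.

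**Conclusion.** The concern holds. Following the liver row and the 6.7.2.2 bullet as written would allow full-dose redosing after a non-serious recurrent grade 3 ALT rise that 6.7.2.1 says must end treatment. Colitis and cutaneous toxicity have the same gap.

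Its extent is 3 of 9 named irAE rows, none with a recurrence rule. For irAEs in the last row of the table, the stricter rule already operates through 6.7.2.4. The number of subjects affected cannot be estimated from the documents and may be small. Sample size, power and error rates are unaffected.

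The conclusion rests on the current text of 6.7.2.1, 6.7.2.2, Table 6-3 with its footnotes, 6.7.2.4 and 7.1. It does not assume that the phase 1a transaminase events were irAEs, recurred or were redosed; the protocol does not say. This is a subject-safety inconsistency that should be corrected.

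**What to change.** 1. Delete the word serious from the 6.7.2.2 bullet, so that it agrees with 6.7.2.1 and the last row of Table 6-3.
2. Add one footnote to Table 6-3: a grade 3 irAE that recurs on rechallenge leads to permanent discontinuation in every row. Keep the present handling of endocrinopathies controlled by hormone replacement (the 6.7.2.2 exception and footnote c).
3. Add the same rule as an item in 6.7.2.4.

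This adopts a rule the protocol already states twice. It can go into the substantial amendment that Sections 2.3.2.2 and 4.2.2 require before phase 1b. The cost is one deleted word, one footnote sentence and one list item. The downside is that a few subjects with a non-serious grade 3 recurrence will stop treatment who might otherwise have continued. There is no analysis cost.
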